10.12. Appendix 12: Abbreviations and Trademarks**LIST OF ABBREVIATIONS**

ADA	Anti-drug antibody
ADE	Adverse Device Effect
AE	Adverse Event
AECOPD	Acute exacerbations of COPD
ALT	Alanine aminotransferase
ASE	All participants enrolled population
AST	Aspartate aminotransferase
ATS	American Thoracic Society
BP	Blood pressure
BIPAP	Bilevel Positive Airway Pressure
CAT	COPD Assessment Test
CIOMS	Council for International Organizations of Medical Sciences
CEC	Clinical endpoint committee
COA	Clinical Outcomes Assessment
CONSORT	Consolidated Standards of Reporting Trials
COPD	Chronic Obstructive Pulmonary Disease
COVID-19	Coronavirus Disease
CPK	Creatine phosphokinase
CPAP	Continuous positive airway pressure
CSR	Clinical Study Report
CRF	Case Report Form
CV	Cardiovascular
DNA	Deoxyribonucleic acid
ECG	Electrocardiography
eCRF	Electronic case report form
ED	Emergency department
eDiary	Electronic diary
EDTA	Ethyl enediamine tetra acetic acid
EGPA	Eosinophilic Granulomatosis with Polyangitis
EQ-5D-3L	EuroQol questionnaire
EQ-VAS	EuroQol-Visual Analogue Scale
E-RS: COPD	Evaluating Respiratory Symptoms in COPD
EXACT	Exacerbations of Chronic Pulmonary Disease Tool
FAAN	Food Allergy and Anaphylaxis Network
FEV ₁	Forced expiratory volume in one second
FSH	Follicle stimulating hormone
FVC	Forced vital capacity
GCP	Good Clinical Practice
GCSP	GSK's Global Clinical Safety and Pharmacovigilance group
GSK	GlaxoSmithKline
hCG	Human chorionic gonadotropin
HbsAg	Hepatitis B surface antigen

HIPAA	Health Insurance Portability and Accountability Act
HIV	Human immunodeficiency virus
HPCL	High performance liquid chromatography
HRQoL	Health related quality of life
HRT	Hormone replacement therapy
IB	Investigator's Brochure
ICF	Informed consent form
ICH	International Conference on Harmonisation
ICS	Inhaled corticosteroid
IEC	Independent ethics committee
IgG	Immunoglobulin G
IL	Interleukin
IP	Interventional Product
IM	Intramuscular
INR	International normalized ratio
IP	Interventional Product
IRB	Institutional research board
IV	Intravenous
IWRS	Interactive Web Response System
IDFU	Instruction Direction For Use
IUD	Intrauterine device
IUS	Intrauterine hormone-releasing system
LABA	Long acting beta ₂ -agonist
LAMA	Long acting muscarinic antagonist
LDH	Lactate dehydrogenase
LFT	Liver function testing
LRTI	Lower Respiratory Tract Infection
LTOT	Long term oxygen therapy
MACE	Major Adverse Cardiovascular Event
MCH	Mean corpuscular hemoglobin
MCV	Mean corpuscular volume
MDI	Metered dose inhaler
MedDRA	Medical Dictionary for Regulatory Activities
mg	Milligrams
MI	Myocardial infarction
mITT	Modified Intent-to Treat
mL	Millilitre
mMRC	Modified Medical Research Council Grading System
MSDS	Materials Safety Data Sheet
NAb	Neutralizing Antibody
NHANES	National Health and Nutrition Examination Survey
NIAID	National Institute of Allergy and Infectious Disease
NIMP	Non-interventional Medicinal Product
NYHA	New York Heart Association
PK	Pharmacokinetic
PD	Pharmacodynamic
PDE-4	Phosphodiesterase-4
PEF	Peak expiratory flow

PGx	Pharmacogenetics
PI	Principal Investigator
PP	Per protocol
prn	As needed
PRO	Patient reported outcomes
QTcF	QT interval corrected with Fridericia's formula
RAP	Reporting and analysis plan
RBC	Red blood cells
SABA	Short acting beta ₂ -agonist
SADE	Serious Adverse Device Effect
SAE	Serious Adverse Event
SAMA	Short acting muscarinic antagonist
SaO ₂	Oxygen Saturation
SC	Subcutaneous
SGOT	Serum Glutamic-Oxaloacetic Transaminase
SGPT	Serum Glutamic-Pyruvic Transaminase
SGRQ	St. George's Respiratory Questionnaire
SGRQ-C	St. George's Respiratory Questionnaire for COPD
SoA	Schedule of Activities
SoC	Standard of Care
SOC	System Organ Class
SS	Safety syringe
SRM	Study Reference Manual
SUSAR	Suspected unexpected serious adverse reactions
ULN	Upper limit of normal
US	United States
USADE	Unanticipated Serious Adverse Device Effect
WOCBP	Woman of childbearing potential

Trademark Information

Trademarks of the GlaxoSmithKline group of companies
CAT

Trademarks not owned by the GlaxoSmithKline group of companies
EQ-5D-3L
E-RS-COPD
EXACT
MedDRA

SAP Amendment 1	16 Nov 2023	Amendment 6 (06-Dec-2021)	
 Definition of Extended Treatment Population updated to include all participants who receive at least one dose of trial medication. Population for selected Study Population and Safety summaries, not Efficacy summaries. 	
 Definition amended to accommodate Extended Treatment population being applied to Study Population or Safety summaries.
			
 Change in handling of intercurrent events of prohibited medication. 	
 Change to handle all occurrences of the intercurrent event of prohibited medication with treatment policy regardless of association with disruptions or restrictions imposed due to the COVID-19 pandemic per feedback from regulatory authority.
			
 Addition of sensitivity analysis for primary endpoint regarding Site_239718. 	
 Due to concerns over data quality at site, sensitivity analysis was added to determine

SAP Version	Approval Date	Protocol Version (Date) on which SAP is Based	Change	Rationale
				effect of site results on primary endpoint.
			
 • Addition of clarification that time to event analyses are carried out for data up to week 104. 	
 • Provide further clarity for analysis.
			
 • Change in safety display presentations to include all data up to Week 104, with specific displays summarizing data separately for participants enrolled for 52 weeks only and those in the Extended Treatment population. 	
 • Facilitate assessment of the overall effect of mepolizumab on safety.
			
 • Updated the SMQ to be used to identify adverse events of pneumonia, this will be Infective Pneumonia SMQ. 	
 • The Pneumonia SMQ is no longer present in the current version of MedDRA.
			
 • Amendment of wording in Immunogenicity section. 	
 • Wording changed to provide further clarity on the testing process.
			
 • Addition of time to first adjudicated MACE analysis section. 	
 • Additional analysis to further explore difference in MACE occurrence in

SAP Version	Approval Date	Protocol Version (Date) on which SAP is Based	Change	Rationale
				the two treatment groups.
			
 • Addition of PK/PKPD analysis. 	
 • To document a PK/PKPD analysis may be conducted if deemed appropriate.
			
 • Addition of details regarding early release of unblinded PK data. 	
 • Early release of PK data to be carried out to aid in refinement of the population PK model.
			
 • Addition of subgroup (symptoms of chronic bronchitis) and removal of subgroups (screening eosinophil categories and other comorbidity). 	
 • Subgroup analyses of subjects with symptoms of chronic bronchitis determined to be of importance. Screening eosinophil categories were deemed unnecessary with screening eosinophil thresholds available. Other comorbidity was deemed not to provide a meaningful analysis.
			
 • Update of countries defining geographic regions. 	
 • Incorporating additional countries participating in MATINEE to their respective

SAP Version	Approval Date	Protocol Version (Date) on which SAP is Based	Change	Rationale
				geographic regions.
			
 • Addition of analyses for Chinese, East Asia, South Korea and India subpopulations. 	
 • Documentation of planned subpopulation analyses.
			
 • Addition of outline of time to withdrawal from IP summary. 	
 • Added for clarity (no change to analysis).
SAP Amendment 2	18 Jul 2024	Amendment 6 (06-Dec-2021)	
 • Addition of baseline definition for CAT and SGRQ questionnaires. 	
 • Added to clarify differences to other baseline definitions.
			
 • Amendment of wording in the sensitivity analysis for primary endpoint section. 	
 • Added clarity on defining the on and off treatment data used for imputation.
			
 • Minor amendments and clarifications added to secondary, pharmacodynamic analyses and other analyses. 	
 • Added to clarify time periods for summaries, populations for summaries and methodologies used.
			
 • Amendment of PK and PKPD analysis objectives to remove covariate exploration. 	
 • Model to be used is well established - covariate selection is not expected to be required and will only occur if original model is not deemed suitable.

SAP Version	Approval Date	Protocol Version (Date) on which SAP is Based	Change	Rationale
			
 Change of subgroup definitions – removed screening eosinophil thresholds, added screening eosinophil categories. Added <40 to age subgroup. 	
 Analysis by screening blood eosinophil threshold no longer required, analysis by screening blood eosinophil categories (<500, ≥500 cells/μL) added as more informative. Additional age subgroup level added for further information.
			
 Subgroup analyses updated to include additional analyses for secondary and other endpoints and shrinkage methods in primary endpoint. 	
 Additional analysis to provide further context behind main analyses.
			
 Amendment of definitions for Chinese, East Asia, South Korea and India subpopulations 	
 Definitions aligned to data categories collected in eCRF.
			
 Minor amendments and clarifications added to study population analyses. 	
 Added to clarify summaries and methodologies used.
			
 Addition of text in demographics section regarding requirements for de-identified summaries. 	
 Added in accordance with new company guidance.

SAP Version	Approval Date	Protocol Version (Date) on which SAP is Based	Change	Rationale
			
 • Addition of eCOA compliance appendix. 	
 • Added in accordance with new company guidance.
SAP Amendment 3	20 Aug 2024	Amendment 6 (06-Dec-2021)	
 • Updates to formatting. 	
 • Applied in line with QC check.
			
 • Addition of further exploratory analyses to assess smoking variables. 	
 • Additional analysis to further explore the impact of smoking in COPD.

1. INTRODUCTION

The purpose of this SAP is to describe the planned analyses to be included in the Clinical Study Report for Study 208657.

1.1. Objectives, Estimands and Endpoints

1.1.1. Objectives and Endpoints

Objectives	Endpoints

Primary
 
 To evaluate the efficacy of mepolizumab 100 mg subcutaneous (SC) compared to placebo, given every 4 weeks in liquid formulation by safety syringe (SS) to COPD participants at high risk of exacerbations despite the use of optimized COPD maintenance therapy. 	
 Annualized rate of moderate/severe exacerbations

Secondary
 
 To evaluate mepolizumab 100 mg SC compared to placebo given every 4 weeks in liquid formulation by SS on additional efficacy assessments, health related quality of life (HRQoL), health care utilization, and symptoms 	
 Time to first moderate/severe exacerbation Proportion of COPD assessment test (CAT) responders (≥ 2 unit reduction in CAT score from baseline) at Week 52 Proportion of St. George's Respiratory Questionnaire (SGRQ) total score responders (measured using the St. George's Respiratory Questionnaire for COPD [SGRQ-C], and defined as ≥ 4 point reduction in SGRQ total score from Baseline) at Week 52 Proportion of Evaluating Respiratory Symptoms in COPD (E-RS: COPD) responders (≥ 2 unit reduction in total score from Baseline) at Week 52 Annualized rate of exacerbations requiring Emergency Department (ED) visit and/or hospitalization

Objectives	Endpoints
Other	

To further investigate other endpoints	
CCI
 
Change from Baseline in pre-bronchodilator forced expiratory volume in one second (FEV1) and forced vital capacity (FVC)CAT responders at Week 24CAT change from baseline at Week 24 and 52SGRQ responders at Week 24SGRQ change from Baseline at Week 24 and 52Proportion of Evaluating Respiratory Symptoms in COPD (E-RS: COPD) responders at Week 24Proportion of E-RS: COPD responders: sub-scales of breathlessness, cough and sputum and chest symptoms at Week 24 and 52Change from Baseline in E-RS: COPD Total Score at Week 24 and 52CCI [REDACTED]
CCI	

Objectives	Endpoints
Safety	

 To evaluate the safety of mepolizumab in participants with COPD 	
 Incidence of AEs/SAEs including systemic reactions. Incidence of adjudicated SAE reports and MACE events (CV death, non-fatal myocardial infarction, and non-fatal stroke) Vital signs including blood pressure (BP), body temperature, pulse rate ECG assessments Mortality (all cause including respiratory and cardiovascular causes of death) Presence of anti-drug antibodies (ADA) to mepolizumab Hematological and clinical chemistry parameters
Health Outcomes	

 To further evaluate the effect of mepolizumab 100 mg SC on health care utilization. 	
 Healthcare utilization for COPD including hospitalization, ED, and physician office/clinic visits
Pharmacokinetics Sub-study: China and US only	

 To evaluate the PK of mepolizumab 100 mg in liquid formulation administered subcutaneously by SS in Chinese participants and to assess potential PK ethnic differences between non-Asian participants in the US and Chinese participants in China 	
 Plasma mepolizumab concentrations

1.1.2. Primary Estimand

The primary estimand is the difference between mepolizumab 100 mg SC and placebo (both added to optimized standard of care) in the annualized rate of moderate/severe exacerbations in participants with COPD experiencing frequent exacerbations and characterized by eosinophil levels, regardless of IP discontinuation/interruption or changes in background medication/starting a prohibited medication, in the absence of COVID-19 pandemic related intercurrent events.

The primary estimand is described by the following attributes:

Population: Participants with COPD experiencing frequent exacerbations and characterized by eosinophil levels

Treatment condition: Mepolizumab 100 mg SC vs. placebo (both as add-on treatment to optimized standard of care)

Variable: Number of moderate or severe exacerbations

Intercurrent events: The anticipated intercurrent events in this trial are discontinuation of interventional product (IP), interruption of 2 or more consecutive doses of IP, use of prohibited medications and change in background medication.

A treatment policy strategy will be used to handle the intercurrent events of discontinuation of IP and interruption of 2 or more consecutive doses of IP when not associated with disruptions or restrictions (e.g. lockdown measures, social distancing) imposed due to the COVID-19 pandemic. Under this strategy exacerbations and time in study will be included in the analysis regardless of the intercurrent event. A hypothetical strategy will be used to handle these intercurrent events when they are known to be associated with disruptions or restrictions imposed due to the COVID-19 pandemic. A treatment policy strategy will be used to handle the intercurrent events of change in background medication and use of prohibited medications.

Rationale for estimand: The use of a hypothetical strategy recognizes any effect on exacerbations due to discontinuation or interruption of 2 or more consecutive doses of IP associated with disruptions or restrictions imposed due to the COVID-19 pandemic, may not have occurred in the hypothetical scenario of the absence of the pandemic.

1.2. Study Design

Overview of Study Design and Key Features	

The diagram illustrates the study design timeline. It shows two parallel paths starting from 'Screening V0' (3-21 days) and 'Screening V1/Run-in' (14-21 days). At 'Screening V1/Run-in', a randomization point 'R' leads to two treatment groups: 'SoC + Mepolizumab 100 mg' and 'SoC + Placebo'. The 'Study Treatment Period' is indicated as lasting from 52 weeks to up to 104 weeks. A 'Study Intervention Product' is administered every 4 weeks, with a timeline showing weeks 0, 4, 8, 12, 16, 20, 24, 28, 32, 36, 40, 44, 48, 52 (Exit V), 56, 60, 64, 68, 72, 76, 80, 84, 88, 92, 96, 100, and 104 (Exit V).
	

^a Participants must have an eosinophil count of ≥ 300 cells/μL at Screening Visit 0 to proceed to Visit 1. They are also required to have a documented historical eosinophil count of ≥ 150 cells/μL in the 12 months prior to Screening Visit 0.
	

^b Participants with no historical eosinophil counts of ≥ 150 cells/μL must have an eosinophil count ≥ 150 cells/μL at Screening Visit 1.
	

^c R = Randomization: Randomization criteria should be assessed at Week 0 (Visit 2) prior to randomization.
	

^d For participants enrolled in the study for 52 weeks, the Exit Visit will be at Week 52, 4 weeks after the last dose.
	

^e For participants receiving study treatment beyond 52 weeks, the Exit Visit will be at Week 104 or aligned to the date the last randomized participant is scheduled to complete their Week 52 Exit Visit, whichever is sooner, see Protocol Section 4.4. The Exit Visit will be 4 weeks after the last dose.
	
Design Features	
This is a multi-center, randomized, placebo-controlled, double-blind, parallel group trial evaluating mepolizumab 100 mg compared with placebo given every 4 weeks as a liquid formulation in a pre-filled safety syringe through SC injection as an add-on to optimized maintenance COPD therapy in participants with COPD characterized by eosinophil levels
 
Study participants will remain in the study for at least 52 weeks and up to a maximum of 104 weeks. All participants will be expected to complete at least 52 weeks of the study. The last randomized participant will be scheduled to complete only 52 weeks of the study. More specifically,

Overview of Study Design and Key Features	
	
 ○ For participants enrolled for 52 weeks, their Exit Visit will occur at Week 52, 4 weeks after the last scheduled dose of IP. ○ For participants enrolled for (or reconsented to) an extended treatment duration beyond 52 weeks, their Exit Visit will be at Week 104 or at a scheduled visit that occurs on or before the date the last randomized participant is scheduled to complete their Week 52 Exit Visit, whichever is sooner. The Exit Visit will occur 4 weeks after the participants last scheduled dose of IP.
Study intervention	
Interventional product will be administered as a single SC injection given every 4 weeks at each study visit (except for the Exit Visit), beginning at the Randomization Visit (Visit 2).
 
Participants are to continue on their baseline optimized COPD medications throughout the study.

Study intervention Assignment	Eligible participants will be randomized 1:1 to receive mepolizumab 100 mg or placebo in accordance with a randomization schedule generated using a validated randomization software, separate randomization schedules will be created for each country.
Blood Eosinophil Inclusion Criteria	Participants must have a blood eosinophil count of ≥ 300 cells/ μ l at Screening Visit 0 and a documented historical blood eosinophil count of ≥ 150 cells/ μ l in the 12 months prior to Screening Visit 0 (or at Screening Visit 1).
Off-treatment data	
The protocol objective is to collect data over the full study period whether participants continue on IP or prematurely withdraw from IP.
 
Unless otherwise specified, data from participants who agree to continue in the study after premature withdrawal from IP will be included in the analysis of efficacy endpoints.

Interim Analysis	No formal interim analyses of efficacy data are planned for this study. See Section 5 for details regarding blinded sample size evaluation.

2. STATISTICAL HYPOTHESES

This study is designed to test the superiority of mepolizumab 100 mg SC vs placebo. The treatment comparison of interest for the primary and secondary endpoints is mepolizumab 100 mg SC vs placebo in the modified Intent-to-Treat (mITT) population, the significance test will be considered statistically significant at the two-sided 5% alpha level (one-sided 2.5%).

2.1. Multiplicity Adjustment

A hierarchical testing procedure will be used to provide strong control of Type I error for multiplicity arising from the primary and multiple secondary endpoints. This will be carried out using a step-down closed testing procedure where inference for an endpoint in the predefined hierarchy will be dependent on statistical significance having been achieved for the previous endpoints in the hierarchy.

For example, for the primary endpoint, mepolizumab will be compared to placebo at a two-sided $\alpha=0.05$ (one-sided $\alpha=0.025$). The next endpoint in the hierarchy (i.e. the first secondary endpoint) will be tested only if the test for the primary endpoint is significant at the one-sided 2.5% level. Testing will continue down the hierarchy for the remaining endpoints in an equivalent manner only if the previous endpoint in the hierarchy achieves statistical significance.

The hierarchy of the primary and secondary endpoints to be tested is as follows:

1. Annualized rate of moderate/severe exacerbations (primary endpoint)
2. Time to first moderate/severe exacerbation
3. Proportion CAT score responders at Week 52
4. Proportion of SGRQ total score responders at Week 52
5. Proportion of E-RS: COPD responders at Week 52
6. Annualized rate of exacerbations requiring ED and/or hospitalization

3. ANALYSIS SETS

Analysis Set	Definition / Criteria	Analyses Evaluated
All Participants Enrolled Population	All participants for whom a record exists on the study database.	Reasons for Screen Failures and Run-in Failures
Modified Intent-to-Treat Population (mITT)	All randomized participants who receive at least one dose of trial medication. Participants will be analyzed by randomized treatment.	Efficacy endpoints
mITT Population excluding past/concurrent Asthma (mITT2)	All participants in the mITT population with no evidence of a past history or concurrent diagnosis of asthma. Participants will be analyzed by randomized treatment.	Primary and secondary efficacy endpoints

Analysis Set	Definition / Criteria	Analyses Evaluated
Safety Population (Safety)	All randomized participants who receive at least one dose of trial medication. Participants will be analyzed based on actual treatment received for more than 50% of treatment administrations.	Safety endpoints
Per-Protocol Population (PP)	All participants in the mITT population not identified as protocol deviators with respect to criteria that are considered to impact the primary efficacy endpoint. The decision to exclude a participant from the PP Population will be made prior to the unblinding of treatment codes.	Supplementary analysis of primary endpoint
Pharmacokinetic (PK)	All participants enrolled in the PK sub-study who received at least one dose of trial medication and for whom at least one pharmacokinetic sample was obtained, analyzed and was measurable. Population for the PK sub-study analysis Data will be reported according to actual treatment received for more than 50% of treatment administrations.	Pharmacokinetics endpoints
Extended Treatment Population	All participants who receive at least one dose of trial medication and who consented to participate in the extended treatment period beyond 52 weeks. Participants within this population are enrolled for up to 104 weeks with variable duration.	Selected Study Population, Efficacy, Safety summaries

4. STATISTICAL ANALYSES

4.1. General Considerations

4.1.1. General Methodology

Confidence intervals will use 95% confidence levels unless otherwise specified.

Unless otherwise specified, continuous data will be summarized using descriptive statistics: n, mean, standard deviation (std), median, minimum, and maximum.

Categorical data will be summarized as the number and percentage of participants in each category.

The efficacy analyses will be based on the mITT/mITT2 population. Where available, data up to Week 104 will be summarized for the mITT/mITT2 Population; where specified, additional displays will present information separately for participants in the

Extended Treatment population. Extended Treatment population study population and efficacy displays will be summarized based on randomized treatment. Details of covariates are provided in Section [4.10.1](#).

4.1.2. Baseline Definition

For the majority of visit-based assessments the baseline value will be the last measurement collected prior to the first dose of interventional product. This will be the pre-dose assessment taken at Visit 2, or if missing the immediately preceding value if available, including from an unscheduled assessment. (Where time is collected, an assessment is valid for use as baseline if the date and time is prior to or the same as the date and time of first dose.)

For CAT and SGRQ assessments, the baseline value is defined as the last measurement taken prior to, or on same date as, first dose of interventional product.

For blood eosinophils, the screening value is defined as the value from the blood sample taken at Screening Visit 0, this pre-dose value is aligned with the blood eosinophil levels required for inclusion into the study. If missing the next available value prior to the first dose of interventional product will be used, however values from the blood sample taken at Screening Visit 1 will not be included in the determination of the screening value. The baseline value will be the measurement defined as the screening value.

For entry into the study, historical blood eosinophils recorded in the 12 months prior to Screening Visit 0 and aligned with the study inclusion criteria are required. For participants who do not have a documented historical blood eosinophil count prior to Screening Visit 0, the value from the blood sample taken at Screening Visit 1 is used.

For data collected every evening using the electronic diary (eDiary), the baseline value will be determined as the average of the 7 days of diary card data collected from the week prior to first dose (i.e., data collected between Day -7 and Day -1 inclusive).

Unless otherwise stated, if baseline data is missing no derivation will be performed and baseline will be set to missing.

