3.1. Pharmacokinetics Sub-study: China and US only

Objective	Endpoint

 To evaluate the PK of mepolizumab 100 mg in liquid formulation administered subcutaneously by SS in Chinese participants and to assess potential PK ethnic differences between non-Asian participants in the US and Chinese participants in China 	
 Plasma mepolizumab concentrations

4. STUDY DESIGN**4.1. Overall Design**

Protocol waivers or exemptions are not allowed with the exception of immediate safety concerns. Therefore, adherence to the study design requirements, including those specified in the Schedule of Activities (SoA, Section 1.3), are essential and required for study conduct.

This is a multi-center, randomized, placebo-controlled, double-blind, parallel group, trial evaluating mepolizumab 100 mg compared with placebo given every 4 weeks through SC injection of a liquid formulation delivered in a pre-filled safety syringe.

It is estimated that approximately 4000 participants will be screened to achieve a target global randomization of approximately 800 randomized participants. The number of randomized participants may increase up to approximately 1400 following blinded sample size re-evaluation (Section 9.2). Eligible participants will be randomized 1:1 to mepolizumab 100 mg or placebo.

During Screening Visit 0, a mandatory haematology blood sample is collected. The Investigator or designee must review the results of the Visit 0 blood eosinophil count prior to initiating Screening Visit 1. Participants with eosinophil count less than 300 cells/ μ L cannot proceed to Screening Visit 1 and will be considered a screen failure. Participants must also have a documented historical eosinophil count of $\geq 150/\mu$ L in the 12 months prior to Screening Visit 0 and the historical eosinophil count must not have been measured during a COPD exacerbation. Participants with no documented historical eosinophil count of ≥ 150 cells/ μ L must meet this threshold based on the Screening Visit 1 assessment in order to return for Visit 2 (Inclusion Criteria, Section 5.1).

Investigators are required to thoroughly review participants' medical records to identify historical eosinophil counts. It is only in the absence of documented records will eosinophils measurement at Screening Visit1 be considered.

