5. STUDY POPULATION

5.1. Inclusion Criteria

Participants are eligible to be included in the study only if all of the below criteria apply. Further details pertaining to the Inclusion Criteria can be found in the SRM.

Age

1. Participant must be at least 40 years of age at Screening Visit 1

Blood eosinophils

2. A peripheral blood eosinophil count of ≥ 300 cells/ μL from the hematology sample collected at Screening Visit 0

AND

A documented historical blood eosinophil count of ≥ 150 / μL in the 12 months prior to Screening Visit 0 that meets the following: It must have been measured between 12 months and 1 month prior to Visit 0, and it must not have been measured within 14 days of a COPD exacerbation.

Participants with no documented historical blood eosinophil count of ≥ 150 cells/ μL must meet this threshold based on the Screening Visit 1 assessment in order to return for Randomization Visit 2.

Type of Participant and Disease Characteristics

3. **COPD Diagnosis:** Participants with a clinically documented history of COPD for at least 1 year in accordance with the definition by the American Thoracic Society/European Respiratory Society [Celli, 2004]
4. **Severity of COPD:** Participants must present with the following:
 - A measured pre- and post-salbutamol FEV₁/FVC ratio of < 0.70 at Screening Visit 1 to confirm the diagnosis of COPD

- A measured post-salbutamol FEV₁ >20% and ≤80% of predicted normal values calculated using NHANES III reference equations [[Hankinson, 1999](#); [Hankinson, 2010](#)] at Screening Visit 1.

5. History of Exacerbations: Participants must have a well-documented history (e.g., medical record verification) in the 12 months prior to Screening Visit 1 of:

- Two or more moderate COPD exacerbations that were treated with systemic corticosteroids (intramuscular (IM), intravenous, or oral) with or without antibiotics

OR

- At least one severe COPD exacerbation requiring hospitalization

Note: At least one exacerbation must have occurred while the participant was taking inhaled triple therapy, ICS plus LABA plus LAMA unless documented intolerance or safety risk with either of the two long-acting bronchodilators. If intolerance is documented, ICS plus LABA or ICS plus LAMA would be allowable after discussion with the Medical Monitor.

Note: COPD exacerbation(s) related to laboratory confirmed COVID-19 infection must not be counted as COPD exacerbation(s) for inclusion in the study.

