9.4.3.2. Pharmacodynamic Analyses

Blood eosinophils ratio to Baseline will be analysed using mixed model repeated measures adjusting for Screening, smoking status, geographic region, visit by Screening interaction and visit by treatment group interaction. Data will be log-transformed (\log_e) prior to analysis.

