4.7.1. Definition of Endpoint

Absolute and ratio to screening blood eosinophil counts will be summarized at each visit for the mITT population up to Week 104.

The summary measure of treatment effect will be the ratio of the effect at Week 52 of mepolizumab compared to placebo.

Only data collected while the participant was on-treatment will be used in the analysis (while on-treatment strategy). Blood eosinophil counts taken more than 28 days following last dose will not be included in the analysis.

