
 The estimated means for each treatment group will be calculated from the model using the observed marginal distributions of the sample covariates (OM option in LSMEANS statement). Model-estimates of the absolute mean and mean ratio to baseline will be back-transformed and presented as ratios with corresponding standard errors on the log scale for each treatment group by visit. Estimated treatment differences (Mepolizumab/Placebo) with corresponding 95% CIs and p-values will also be presented. 									

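### The within-arm eosinophil ratios use the Visit 0 selection count as denominator, so regression to the mean overstates the fall in both arms; the between-arm ratio is not biased

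*SAP*

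**What the plan says.** SAP 4.1.2 uses the pre-dose Visit 2 value as baseline for most visit-based assessments but makes an exception for eosinophils: "the screening value is defined as the value from the blood sample taken at Screening Visit 0". Its reason is that "this pre-dose value is aligned with the blood eosinophil levels required for inclusion into the study". It then merges the two terms: "The baseline value will be the measurement defined as the screening value".

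Entry depends on that same measurement. Protocol 4.1 deals with "Participants with eosinophil count less than 300" cells/µL at Visit 0 by making those people screen failures, and inclusion criterion 2 (Protocol 5.1) sets the same threshold. A second criterion asks for at least 150 cells/µL on a historical count ("It must have been measured between 12 months and 1 month prior to Visit 0") or, failing that, at Visit 1.

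The outputs that use this denominator are:

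- SAP 4.7.1, descriptive, to Week 104: "Absolute and ratio to screening blood eosinophil counts will be summarized at each visit".
- SAP 4.7.2, from the MMRM, by treatment group and visit: "Model-estimates of the absolute mean and mean ratio to baseline will be back-transformed".

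SAP 4.7.1 defines the treatment effect as the mepolizumab-to-placebo comparison at Week 52. Protocol 9.4.3.2 words the analysis as: "Blood eosinophils ratio to Baseline will be analysed using mixed model repeated measures adjusting for Screening". The protocol does not say which sample is Baseline for eosinophils.

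**The concern.** A single eosinophil count is the person's usual level plus visit-to-visit variation. Keeping only people whose Visit 0 count reached 300 keeps a surplus of those whose variation was upward that day. Their next count is lower on average, with or without treatment. When the selected count is also the denominator, this surplus enters every later ratio.

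What is at stake is the reading of the per-arm pharmacodynamic results. Placebo would appear to lower eosinophils, and the mepolizumab reduction would look larger than it is. No caveat is planned for these ratios.

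**Working it through.** The documents state no expected ratio and no eosinophil variance, so there is no figure of the plan's own to reproduce. The check is whether the bias follows from the definitions, and how large it is under stated assumptions.

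**Model.** Log count = person mean + independent visit error. Between-person SD is b, within-person SD is w, and s = √(b² + w²). The thresholds of 300 (Visit 0) and 150 (second count) come from Protocol 5.1. The values b = 0.5–0.7, w = 0.35–0.45 and source geometric mean 200 cells/µL are assumptions.

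**Selection on Visit 0 alone, no true change.** With a = ln(300/200)/s and λ = φ(a)/(1 − Φ(a)), the mean log Visit 0 count is raised by sλ above the source mean. A later count keeps only the share b²/s² of that rise. Hence

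ratio to Visit 0 = exp(−(w²/s)·λ).

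- b = 0.5, w = 0.45: s = 0.673, a = 0.603, λ = 1.217, w²/s = 0.301; ratio = exp(−0.366) = 0.693.
- b = 0.7, w = 0.35: s = 0.783, a = 0.518, λ = 1.154, w²/s = 0.157; ratio = exp(−0.181) = 0.835.

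These are the two extremes of the assumed grid. The ratio equals 1 only if w = 0, so the direction does not depend on the assumptions.

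**Adding the second criterion.** Simulation with an independent second count of at least 150 gives 0.715 and 0.845 at the same two corners, so this criterion offsets little.

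**Effect on the mepolizumab arm.** Take an assumed true ratio of 0.20. Then 0.20 × 0.715 = 0.143 (a fall of 85.7%) and 0.20 × 0.845 = 0.169 (83.1%), against a true 80%. With Visit 0 selection alone, 0.20 × 0.693 = 0.139 (86.1%) and 0.20 × 0.835 = 0.167 (83.3%).

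**Wider assumptions.** With source median 150–250, total log-SD 0.7–0.8, single-count reliability 0.6–0.9 and both criteria, the placebo ratio runs from 0.67 to 0.94. At median 200, SD 0.7 and reliability 0.7, the geometric mean is 469 at Visit 0 and 372 at Visit 2, a ratio of 0.79.

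**Does the covariate remove it?** The planned MMRM includes log baseline and a visit-by-baseline term. Least-squares means taken at the sample's own covariate mean still return each arm's mean log ratio. A one-visit ANCOVA version, in that last setting and with the denominator also used as covariate, confirms this:

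| Denominator | Placebo | Mepolizumab | Mepolizumab/placebo |
|---|---|---|---|
| Visit 0 | 0.79 | 0.158 | 0.20 |
| Visit 2 | 1.00 | 0.200 | 0.20 |

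The between-arm ratio is the same either way, because the bias multiplies both randomized arms equally.

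**Is an unselected count available?** Yes. The critical Visit 2 procedures in Protocol 8 include hematology, and no eosinophil entry criterion uses that sample.

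**The case against.** The choice of Visit 0 is explicit and reasoned. The same screening count feeds the exploratory model (SAP 4.2.5) and the eosinophil subgroups (SAP 4.10.1), so a single reference value is tidy. SAP 4.7.1 and the endpoint line of 4.7.2 call the quantity a ratio to screening, which is an accurate label. The SAP does not treat a within-arm change as a treatment effect, the concurrent placebo arm would reveal the regression, and absolute counts are also planned by arm and visit.

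Much of this stands, and it is why the point is minor. But alignment with inclusion justifies Visit 0 as a covariate and subgroup variable; it does not justify it as the denominator of change. The placebo arm and the absolute counts let a careful reader notice the bias without correcting the ratios that are reported. SAP 4.7.2 also presents the model results as ratios to baseline, where the reader has no cue that baseline is the selection count.

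A reader might infer that the SAP overrides the protocol, that using Visit 2 would restore protocol text, and that SAP Table 1 should have listed a change. The documents do not support that. Protocol 9.4.3.2 names Baseline and Screening separately, which suggests two values, but it never defines eosinophil Baseline as Visit 2, and Protocol 9.4 leaves analysis detail to the analysis plan. Filling an open definition is not clearly a departure.

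**Conclusion.** The point holds for the within-arm ratios only. As the plan is written, they overstate the eosinophil fall in both arms. The direction is certain provided counts vary at all within a person. The size is assumed: placebo about 0.72–0.85 with no true change (0.69–0.84 without the second criterion), and a true 80% reduction reading as about 83–86%. Under the wider assumptions the placebo range is 0.67–0.94.

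It would be wrong to conclude that the estimated treatment effect on eosinophils is inflated: the Week 52 mepolizumab/placebo ratio is not biased. The analysis lies outside the testing hierarchy in SAP 2.1, so the primary endpoint, type I error and power are untouched. This is a cheap improvement to reporting.

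**What to change.** In SAP 4.1.2 and 4.7, define the within-arm ratios, descriptive and model-based, against the pre-dose Visit 2 count, falling back to Visit 0 when that count is missing. Keep the Visit 0 count as the screening covariate and for subgroups and exploratory modelling. Use one term for each quantity throughout 4.7. The between-arm comparison can stay as specified. In simulation, the Visit 2 denominator returns a placebo ratio of 1.00 when nothing has changed and recovers the assumed 0.20 on mepolizumab.

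The cost is SAP wording and programming on data already collected, a fallback rule (participants who use it keep the bias), and a denominator that differs from the screening value used elsewhere. If Visit 0 is kept as denominator, the minimum is a footnote saying that the within-arm ratios include regression to the mean and that only the between-arm ratio should be interpreted.
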